provide evaluable information on the infants. In addition, we expect that cord blood data will not be obtainable or analyzable for a certain percentage of live births resulting in missing data on two of the primary outcomes. To account for this, we plan on initially consenting approximately 525 *RAPIDIRON Trial* participants (~175 per arm). Because Aims 1 and 2 answer different essential research questions, the study is powered with a type I error rate of 0.05 for each of those aims.

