We propose to conduct a total of four primary hypothesis tests for Aim 1. Two of those tests will be conducted on data collected at birth with separate tests comparing offspring born to mothers across both IV iron arms to those born to mothers in the oral arm with respect to hemoglobin level and log-transformed ferritin levels at birth. If either of those tests at birth show differences between the two arms, the comparable tests will be conducted at 4 months post-delivery. In all cases, the null hypothesis is that the mean across the IV arms is the same as that in the oral iron arm. To control the type I error rate across these two tests, the alpha level for each individual comparison will be 0.025. Although information on the likely effect sizes for the proposed intervention are insufficient to provide explicit estimates of power for this study, limited comparisons of infant hemoglobin levels in south Asian and Africa suggest that the differences in both hemoglobin levels and log ferritin levels in infants born to mothers with and without IDA differ by at least 0.8 standard deviations. Because we want to assure that this intervention is powered to detect effects somewhat smaller than that observed in mothers with and without IDA, we want to assure that this study has sufficient power to detect an effect that is in the range of 0.3 to 0.4 standard deviations. We anticipate that approximately 85% of the enrolled sample will provide data for our primary iron outcomes at birth. Thus, we estimate a sample size of at least 441 infants (147 per arm) will provide information at birth with a slightly higher number at 4 months as this time is not subject to difficulties with obtaining data from the cord blood at delivery. When evaluated in the context of the proposed mixed effects model where we assume an intraclass correlation coefficient of 0.5, a sample size of 147 per arm (294 IV iron vs. 147 oral) gives more than 80% power to detect a difference in means at birth of 0.31 standard deviations at the alpha=0.025 level. Since demonstrating the effects at 4 months requires that the hypothesis tests at birth reject the null hypothesis, the overall study power to detect a difference of 0.3 standard deviations or greater at 4 months is greater than 80%.

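### The Aim 1 sample-size text gives required rejection at birth as the reason 4-month power exceeds 80%, but at a fixed alpha that requirement can only lower power; per analyte it is about 64% to 74%

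*Combined protocol and SAP*

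**What the plan says.** All of this is in Section E, Sample Size, in the Aim 1 text. Hemoglobin and log ferritin are each tested at birth, pooled IV arms against oral, and "the alpha level for each individual comparison will be 0.025". The 4-month tests are conditional: "If either of those tests at birth show differences between the two arms, the comparable tests will be conducted at 4 months post-delivery".

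For birth, the plan says that 147 per arm, analysed in a mixed model with an intraclass correlation of 0.5, "gives more than 80% power to detect a difference in means at birth of 0.31 standard deviations at the alpha=0.025 level". It expects 441 infants at birth, "with a slightly higher number at 4 months as this time is not subject to difficulties" with cord blood, but gives no 4-month number. The upper limit is the number consented: "we plan on initially consenting approximately 525" women, about 175 per arm.

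The power statement for 4 months then reads: "Since demonstrating the effects at 4 months requires that the hypothesis tests at birth reject the null hypothesis", and from this it concludes that "the overall study power to detect a difference of 0.3 standard deviations or greater at 4 months is greater than 80" per cent.

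The Primary Data Analysis text repeats the 0.025 level for the 4-month comparison and does not mention the birth condition.

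**The concern.** The sentence runs the logic backwards. Requiring an earlier rejection adds a hurdle, so at the same alpha and sample size it cannot raise the power of the later test. The claim also sits badly beside the plan's own birth figure, where 0.31 SD is needed to reach about 80% with no prior condition. The 4-month claim is for a smaller effect with a condition added.

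Two terms needed to check the figure are undefined:

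- **The birth condition.** The text can mean that each analyte opens its own 4-month test, or that either analyte opens both.
- **Overall power.** It can mean power for each analyte, or for at least one of the two.

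The 4-month tests are two of the four primary Aim 1 tests, and primary hypothesis 1 names both hemoglobin and ferritin at both times. If the stated power is too high, a reader will take a non-significant 4-month result as stronger evidence against an effect than the design supports.

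**Working it through.** **Inputs from the plan.** 294 IV vs 147 oral; alpha 0.025 per test; correlation 0.5 between birth and 4 months in the same infant. Sidedness is not stated. The null is equality ("In all cases, the null hypothesis is that the mean across the IV arms is the same as that in the oral iron arm"), so I take the tests as two-sided.

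**Assumptions.** The effect is 0.30 SD at both times. The hemoglobin-log ferritin correlation is not given; I use 0 to 0.7. The correlation between one analyte at birth and the other at 4 months is taken as the product of the analyte and time correlations.

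**1. Reproduce the birth figure.** SE = √(1/294 + 1/147) = 0.1010 SD, and z(0.9875) = 2.241. At 0.31 SD, 0.31/0.1010 = 3.069, so power = Φ(3.069 − 2.241) = 79.6%. If 155 per arm are seen at 4 months, the mixed model gains a little precision at birth and power is 80.2%. This matches the plan. A one-sided 0.025 test would give 86.6%, so the match supports the two-sided reading.

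**2. The 4-month test with no condition.** At 0.30 SD, 0.30/0.1010 = 2.970, so power = Φ(2.970 − 2.241) = 76.7%. For 80%, the number per arm is 1.5 × [(2.241 + 0.842)/0.30]² = 158.4, so 159.

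**3. Each analyte opens its own 4-month test.** Power is P(Z_birth > 2.241 and Z_4mo > 2.241), bivariate normal with both means 2.970 and correlation 0.5. The result is 64.2%.

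**4. Either analyte opens both.** With A and B the two analytes and 0 and 4 the times, power for A is P(A0,A4) + P(B0,A4) − P(A0,B0,A4). For independent analytes this is 0.6424 + 0.7668² − 0.6424 × 0.7668 = 0.6424 + 0.5880 − 0.4926 = 73.8%. For analyte correlation 0.5 and 0.7, the multivariate normal gives 71.1% and 69.7%.

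**5. More infants at 4 months.** These figures take 147 per arm seen at both times and the rest at 4 months only, with generalised least squares estimates. Ranges are for analyte correlation 0.7 to 0.

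| Per arm at 4 months | No condition | Own analyte | Either analyte |
|---|---|---|---|
| 147 | 76.7% | 64.2% | 69.7% to 73.8% |
| 155 | 79.1% | 66.1% | 71.8% to 76.1% |
| 160 | 80.4% | 67.1% | 73.0% to 77.5% |
| 175 | 84.1% | 70.0% | 76.3% to 81.1% |

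**6. Larger birth effect.** With 0.40 SD at birth, 0.30 SD at 4 months and 147 per arm, power is 75.2% (own analyte) or 76.2% to 76.6% (either).

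**7. At least one analyte significant at 4 months.** At 147 per arm and 0.30 SD at both times, power is 76.6% to 87.2% (own analyte) or about 77% to 90.3% (either).

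**8. Effect at both times needed for 80% per analyte at 147 per arm.** About 0.345 SD (own analyte) or 0.319 to 0.330 SD (either).

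**The case against.** The best defence is that overall study power means the chance of showing an effect on at least one analyte. For analyte correlations of 0 to 0.5, that power is 80.2% to 90.3% at 147 per arm, so the printed figure would be true. This stands as a possible reading. The text does not adopt it, the figure falls to about 77% at correlation 0.7, and the birth condition would still not be the reason for it.

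A second point is that the headline inputs are unfavourable. The plan expects somewhat more than 147 per arm at 4 months, and cord blood measures fetal loading directly, so a larger birth effect is plausible. That narrows the gap: with 0.40 SD at birth, 80% per analyte needs about 159 to 165 per arm at 4 months. The plan commits to no such number. With 0.30 SD at both times, 80% per analyte is reached only if essentially all 175 consented per arm are seen, either analyte opens both tests, and the analytes are close to independent.

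Third, the ordering of tests does buy something: it avoids a further split of alpha. Four unconditional tests at 0.0125 each would have 68.2% power per analyte at 147 per arm. That is a fair argument for the design. It does not support the sentence, which holds alpha at 0.025.

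Fourth, the plan targets 0.3 to 0.4 SD and admits that effect-size information is thin. At 0.35 SD, power per analyte is about 82% to 88%. The shortfall is therefore at the bottom of the range, but the printed claim is made at 0.3 SD.

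The sentence may come from conditional power: given rejection at birth for the same analyte, 4-month power is 64.2/76.7, about 84%. That is not overall power.

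**Conclusion.** The concern holds. The inference is invalid under any assumptions about effect or correlation, provided alpha and sample size are fixed. Per analyte, at 0.30 SD at both times, 147 per arm, two-sided 0.025 and correlation 0.5, power is 64.2% (own analyte) or 69.7% to 73.8% (either). The chance of missing a real 4-month effect is therefore about 26% to 36%, not under 20%. The upper end of the power range depends on independent analytes as well as on the choice of rule.

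The power sentence could also be read as requiring both birth tests to reject. That conflicts with the testing rule a few lines above it, and would lower power per analyte to about 49% to 57%.

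The claim of more than 80% can be true for at least one analyte, but the plan does not define power that way. No estimate or test is invalidated. What is wrong is the stated power for two of the four primary Aim 1 tests. It should be fixed.

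**What to change.** 1. State whether a 4-month test opens on rejection at birth for the same analyte or for either analyte, and repeat the rule under Primary Data Analysis. The choice belongs to the authors.
2. Define overall power: per analyte, or at least one analyte.
3. Delete the inference from the birth condition to power above 80%. Give the joint power for the chosen rule, with its assumptions: effect at each time, number per arm at 4 months, within-infant correlation, and hemoglobin-ferritin correlation.

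At 0.30 SD at both times and 147 per arm, the figure would be about 64% per analyte (own analyte), about 70% to 74% per analyte (either), or about 77% to 90% for at least one analyte.

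The cost is wording and one recalculation. On the per-analyte readings the stated power becomes less favourable. No participants are added.

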An analysis of maternal hematologic indices will be completed when all women have passed the 12 month collection period. This analysis will include all available maternal blood data through 12 months. Based on the results of this analysis, the research team may decide to suspend collection of maternal blood at 24 months. Other extensive interim analysis is not planned. However, typical study monitoring activities could trigger such an analysis for one or more of the following reasons: recruitment proves problematic, making it difficult to perform an adequate number of tests and obtain measurements at desired time points; study withdrawals, investigator-recommended discontinuations, or 'loss-to-follow-up' among children enrolled in the study are significant; and/or there is a poor ratio for data obtained vs. data expected for important study variables. If undertaken, the interim analysis would consider if continuation

of the study, despite existence of challenges such as those mentioned, could nevertheless provide enough valid evidence to judge whether the primary study hypotheses remain valid. If the answer is no, the study could be prematurely stopped.

Safety Analyses

All safety analyses will be descriptive based on the safety cohort with no planned formal inference for safety. All adverse events will be summarized by system organ class by arm with point and interval estimates of the risk of each of these events estimated by either exact binomial methods or normal approximations to the binomial as appropriate for the incidence of the event.

Descriptive statistics will also be generated for maternal and infant mortality and for incidence of serious adverse events (SAEs).

Analysis Cohorts

Intent-to-treat (ITT) cohort: study participants (mothers or infants, depending on the particular analysis) will be included using group assignments for the mother as randomized.

Delivery iron status cohort: Analyses that examine outcomes as a function of delivery iron status will include enrolled maternal participants with sufficient delivery data to determine iron status of the infant at delivery.

Assignment of participants into the various cohorts will be determined based on a masked data review prior to initiation of analysis.

F. Gender/Minority/Pediatric Inclusion for Research

The parent study, the *RAPIDIRON Trial*, was initiated in mid-March 2021 in two states of India; thus, its participants are classified as adult, female Asians and their offspring will likewise be considered Asian. Pregnant women utilizing facilities classified in the Indian public health system as primary or community health centers will have the opportunity to participate if they meet specified eligibility criteria. No pregnant woman will be excluded because of socioeconomic status or other personal characteristic that could be considered to qualify such women as minorities. Similarly, the offspring for whom consent will be sought – from the *RAPIDIRON Trial* participant – will not be excluded due to minority or family economic status. Additionally, there will be no gender bias in the inclusion of the participants for this follow-up study. By definition, newborn infant participants are children (thus, there is pediatric inclusion).

G. Human Subjects

1. Study Population

Participants of this study are mother-infant dyads consisting of women, residing in Karnataka state, who were randomized and treated for IDA during the *RAPIDIRON Trial* and their newborns.

Inclusion Criteria:

- Informed consent of the *RAPIDIRON Trial* participant for their study inclusion and that of their offspring for the *RAPIDIRON-KIDS Study*
- Expressed intent of the *RAPIDIRON Trial* participant to remain in the designated Karnataka research area for delivery and during the follow-up period for the *RAPIDIRON-KIDS Study* to enable participation in study visits
- For the offspring – live-born singleton infants of Karnataka maternal participants randomized and treated in the *RAPIDIRON Trial*, if consent is provided by the mother

Exclusion Criteria:

- Unwillingness of maternal participant to provide *RAPIDIRON-KIDS Study* consent for herself and her offspring

2. Sources of Research Material

Results of blood tests will be a source of data for this research. The *RAPIDIRON Trial* will provide the hemoglobin (Hb) for the last blood sample taken for a participating woman prior to delivery, as well as iron indices at 6 weeks postpartum. The *RAPIDIRON Trial* protocol also calls for the collection of cord blood subsequent to delivery to assess Hb, transferrin saturation, ferritin, and reticulocyte indices of the newborns. For the purposes of the *RAPIDIRON-KIDS Study*, blood samples of approximately half a teaspoon of blood (2-3 mL) will be collected from the mother at the 4, 12, and 24 month study visits, and 0.5 – 0.8 mL collected via heel stick from the offspring at the 4 and 12 month study visits to determine hemoglobin and iron indices.

The visits for the *RAPIDIRON-KIDS Study* also include performing assessments as listed in Table 1 (some of which overlap with the parent study). As part of the *RAPIDIRON Trial*, infant weight and length will be collected at birth, and maternal reports of labor and delivery practices and complications will be recorded. For the *RAPIDIRON-KIDS Study*, we will collect child head circumference at birth and administer the ICFI to the mother/parent to collect information regarding breastfeeding practices, general nutritional intake, and iron supplementation. Additionally, we will collect child height and head circumference at 6 weeks, 4, 12, 24, and 36 months of age. We will administer the ICFI at 6 weeks, 4, 12, and 24 months of age. We will also collect child weight at 4, 12, 24, and 36 months of age (as it will be collected via the *RAPIDIRON Trial* at the 6-week visit). The World Health Organization Disability Assessment Schedule 2.0 (WHODAS 2.0) will be utilized to assess the mother's quality of life when the offspring has reached 6 weeks (as part of the *RAPIDIRON Trial*), 4 months, and 12 months of age. Data will also be collected to monitor rates of transfusion and hospitalization among the maternal participants through the end of the study.

As part of the *RAPIDIRON-KIDS Study*, we will conduct a variety of neurobehavioral assessments with the offspring using validated tools, as follows:

- The Bayley Scales of Infant Development (BSID) is a validated tool for assessment of general developmental abilities which is routinely used in large-scale randomized controlled trials (RCTs) to detect deficits in the motor, language, and cognitive domains. This will be conducted at the 24 and 36 month visit.
- The Ages & Stages Questionnaire, 3rd Edition (ASQ-3) is designed to obtain parental input regarding a child's general developmental milestones. For the ASQ-3, mothers provide answers for the questionnaires, and this will be conducted at the 12 month visit.
- The Preferential Looking Time test assess recognition learning and memory by presenting an infant with an object (or a picture of an object) which they are expected to familiarize themselves with. After a time delay, the familiar object is presented along with a novel object, and the time spent observing each object will be measured (with the expectation that they will spend more time observing the novel object to demonstrate recognition memory). This test will be conducted at the 4 and 12 month visits.
- The Behavioral Rating Scale is coded from a video recording of the offspring undergoing the BSID and assesses engagement, tractability, exploration, hesitancy, and activity level. At the 24-month visit, the child will be recorded undergoing the BSID. Trained staff will code the recordings, with a random sub-sample sent to the Masonic Institute of the Developing Brain to be coded again for quality assurance.
- The Child Behavior Checklist for Ages 1.5 to 5 years (CBCL/1.5-5) is completed by the parent/caretaker who spends the most time with the child, and involves rating items on a three-

point Likert scale assessing internalizing and externalizing behaviors. This requires 10-20 minutes for completion and will be conducted at the 24 and 36 month visits.

- The India Scale of Assessment for Autism is similar to the standard screening tool for autism (Modified Checklist for Autism in Toddlers) and has been validated for the Indian population. This will be conducted at the 36 month visit.

Personnel will be trained prior to initiating assessments and will be required to achieve competence in scoring performance, recording results, and completing and submitting data forms for entry into the data management system. Arrangements will be made for the use of suitable space for assessments and quality monitoring will ensure appropriate conduct of the research. Specific data forms will be used for recording data for participating mothers and offspring, and these forms will be available at locations where needed.

3. Recruitment and Consent Procedures

Community sensitization occurred in communities served by the primary and community health centers participating in the *RAPIDIRON Trial* and additional sensitization will occur in the Karnataka research area to promote awareness of plans for implementation of the *RAPIDIRON-KIDS* study. Sensitization generally consists of research staff holding meetings with community leaders, health officials, and other relevant parties. Accredited Social Health Activities (ASHAs) who live within the communities that constitute the research area may be asked to participate in the study (with authorization of the supervising health official), for example, by accompanying a mother and child to a center of engagement in the screening and consent process, or by ensuring that a participating child and mother keep an appointment for a blood draw or for developmental testing. ASHAs receive incentive-based fees for their work associated with government-defined responsibilities which include transporting mothers and children to health facilities for needed care. In prior situations when approval has been granted for their involvement in research designed to improve women's and children's health, their assistance has been a key factor in the success of the research.

ASHAs who have received education relevant to anemia and iron deficiency can be an additional source of information about this study. However, consent will be obtained by a trained facility health care provider or research staff member who is a physician or other certified health care provider having adequate health-related training to provide information about the nature and purpose of the study and is able to answer questions during the consent process.

Current *RAPIDIRON* participants will be given information about the study and an opportunity to consent as early as the 6th *RAPIDIRON* visit (26-30 weeks of pregnancy) and will be able to provide consent up until delivery, as long as they are not yet in active labor.

4. Description of Risks, Assessment of Likelihood and Seriousness

This *RAPIDIRON-KIDS Study* involves no intervention, and thus the risks associated with study participation can be considered minimal but include the possibility that drawing blood for analysis could cause bruising and, rarely, infection. No serious risks are associated with the various assessments indicated in Table 1, although some discomfort or anxiety on the part of the child or a mother cannot be ruled out but can often be ameliorated by individuals appropriately trained to conduct assessments.

5. Procedures for Protecting Against or Minimizing Potential Risks

Care will be taken to reduce the risk of bruising. Sterile technique will be utilized during blood draw to reduce risk of infection. Personnel conducting sociodemographic, neurodevelopmental, and other assessments will have adequate background and relevant training to ensure competency.

6. Potential Benefits, Importance to Participants and Others

The possible benefits to participants may be earlier diagnosis of iron deficiency due to a screening schedule which encompasses more monitoring opportunities than is associated with usual practice. Both mothers and infants whose hemoglobin values fall below a pre-designated cutoff will be appropriately referred as per standard of care. Further, if neurodevelopmental testing indicate possible disorder, parents will be told about resources for confirming a diagnosis and for seeking supportive services (if they exist locally).

In combination with the parent study, the *RAPIDIRON Trial*, it is hoped that this follow-up study will result in the expanded use of a more effective approach for the treatment of IDA and decrease the risk that offspring will suffer the consequences of an ineffective IDA treatment approach. Further, if the IV iron treatment approach is determined feasible and adopted widely as a frontline treatment for IDA in pregnancy, the number of future beneficiaries of these studies can be multiplied.

7. Discussion of Why Risks are Reasonable in Relation to Benefits

The *RAPIDIRON-KIDS Study* can be considered an observational study with minimal risk. However, if the study results in earlier diagnosis and earlier treatment of iron deficiency, and delivery of services to address developmental disorders, then participating children and mothers may receive greater benefit than would be the case if such problems were recognized later in life.

H. Data and Safety Monitoring Plan

1. Data and Safety Monitoring Plan (DSMP)

For the *RAPIDIRON-KIDS Study*, a serious adverse event (SAE) involves mothers (and their infants) who were treated for iron deficiency anemia as participants in the *RAPIDIRON Trial* and who provide consent for themselves and their offspring to participate in the *RAPIDIRON-KIDS Study*. To qualify as an SAE, the event must fulfill at least one of the criteria below:

- Results in a maternal or neonatal death, or fetal death >20 weeks gestation;
- Is life-threatening;
- Requires an unanticipated hospitalization or prolongs an existing hospitalization
- Results in persistent or significant disability or incapacity; or
- Represents other serious or unexpected adverse events that a study investigator feels should be reported, including need for resuscitation.

Specific forms will be utilized to report an SAE. For an SAE, the reporting form should be sent to the person designated to receive it within 7 days of the notification of the event. Reportable adverse and serious adverse events will be shared with the DSMB. If there is an unanticipated problem recognized as posing a risk to participants or others and it is likely to reoccur, a designated researcher should obtain additional information on the unanticipated event and compile a report to forward to the study Principal Investigator, Chief Quality and Safety Officer, and the Chair of the DSMB. The Chair will review the report and determine significance of the event to the study and the need for action to avoid harm to participants. The Chair may put the report on the agenda of the next DSMB meeting or communicate with members to address the unanticipated problem sooner.

At each scheduled DSMB meeting after completion of the primary randomized trial, SAE data and a report summarizing retention and participant status will be prepared for review and discussion. Following its deliberations, the DSMB will issue any recommendations it may have and specify that the study should continue based upon absence of safety concerns or concerns about data quality or excessive loss-to-follow-up.

2. Data and Safety Monitoring Board (DSMB)

It is envisioned that the independent data and safety monitoring for this *RAPIDIRON-KIDS Study* will be provided by the same Data and Safety Monitoring Board (DSMB) that oversees the primary randomized controlled *RAPIDIRON Trial*. The Board Chair has expertise in high-risk obstetrics and global health research. The other members have expertise that spans obstetrics and gynecology, neonatology/pediatrics, biostatistics, clinical trials design and implementation, and clinical management of anemia. All members of the DSMB are free of significant conflicts of interest (i.e., financial, intellectual, professional, or regulatory) to enable performance of their duties in an unbiased manner.

The duties to be performed by the DSMB specific to this study include:

- Review all serious adverse events (SAEs) and unanticipated problems that infants and mothers incur to determine if they pose ongoing risk for continuation in the *RAPIDIRON-KIDS Study*;
- Assure that the *RAPIDIRON-KIDS Study* activities are conducted in a manner to minimize risk to infants and mothers and assess maternal and infant burden of participation to confirm that the study is conducted in a safe and ethical manner;
- Assess data quality and participant retention to assure that the benefit of study continuation is consistent with participant burden; and
- Prepare reports that outline DSMB recommendations and provide them to the study Principal Investigator, the Senior Foreign Investigator, and the Chief Quality and Safety Officer.

After data from the primary RCT have been collected for outcomes through 42 days post-delivery (which constitutes completion of the clinical component of the *RAPIDIRON Trial*), the DSMB will continue to meet approximately annually to review the data from this follow-up study. The DSMB may revise the annual meeting schedule if the workload justifies. If a scheduled meeting is considered too remote to review an SAE and determine relevant action, information may be distributed to DSMB members via email and input sent to the DSMB Chair who can communicate a recommendation representing consensus among DSMB members to senior key personnel of the study. The Chief Quality and Safety Officer will be the intermediary in supplying appropriate data to the DSMB for review.

I. Literature Cited

